## Purpose

This study is designed to test the efficacy of a novel electrical stimulation platform named the Tennant Biomodulator designed by AVAZZIA to accelerate wound healing, reduce pain and improve mobility in patients with diabetes and lower extremities ulcers/wounds after four weeks of therapy. In addition,

The objective of the study is to examine effectiveness of transcutaneous electrical stimulation (TENS) as an adjunct therapy to improve wound outcomes among people with plantar ulcers. Our hypotheses are:

H1: TENS is effective to relieve pain in particular during night and during dressing change

H2: TENS is effective to increase skin perfusion

H3: TENS is effective to speed up wound healing weekly rate

H4: TENS is effective to improve mobility :

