**Aim2: Examine long-term benefit of daily home use of lower electrical stimulation (long-term benefit):** Eligible participants will be randomized (ratio: 1:1) to either active (active group, n=20) or sham (sham group, n=20) therapy group. After receiving education, both groups will receive a home-based electrical stimulation system (Tennant Biomodulator device) for daily use at home up to 4 weeks. The duration of each treatment session per day will be one hour. The active group will receive an active electrical stimulation device. The control group will receive an identical device but without active electrical stimulation output. Participants and physicians who are treating the wound would be blinded to the type of device assignment. The study coordinator will be aware of assignment (active device or sham device). Each unit will be coded with a unique identification number. At the last visit, the study coordinator will reveal their group allocation. Since participating patients will have moderate-to-severe peripheral sensory neuropathy, they will be unable to determine via “feeling” whether or not they were receiving electrical stimulation. Patients will visit the clinic on weekly basis up to 4 weeks for assessing outcomes. The primary outcomes include changes in speed of wound healing and changes in plantar sensation. Secondary outcomes include patients self-report outcomes (e.g., pain, sleep quality, and quality of life), changes in mobility (e.g. physical activities and gait), and adverse outcomes (e.g., infection, amputation, etc.). Skin perfusion will be assessed similar to the method described in the Aim 1. Plantar sensation will be assessed using vibratory

perception threshold. Balance will be assessed using wearable sensors (BalanSENS, Biosensics LLC, MA, USA), mobility will be assessed using wearable sensors (PAMSys, Biosensics LLC, MA, USA), sleep quality will be assessed using PSQI questionnaire, and quality of life will be assessed using PROMIS Global.

Our hypotheses are

*H2:* Weekly speed of wound healing would be higher in the active group compared to the shame group

*H3:* Plantar sensation is improving in the active group in response to active therapy.

*H4:* Patient-reported outcomes and other secondary outcomes will be improved in the active group.

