### **Sample size estimation:**

The estimated number of study subjects is 40. The sample size for the short-term effect (immediate changes in skin perfusion) was estimated to achieve 85% power when comparing to baseline values, using assumed rates of 50% and 10% improvement, respectively. A two-sided test of results in evaluable subjects (qualified for analyses of efficacy on immediate changes on skin perfusion) will provide the specified power at a 5% significance level. Sample size calculations resulted in a requirement for a total of 27 subjects. The sample size for long term benefit was estimated based on our previous study (Najafi et al, Diabetes Sci & Tech, 2017) in which effectiveness of daily use of electrical stimulation to improve balance was examined using a randomized controlled trial model. An effect size of greater than Cohen’s  $d=1.35$  was observed for improvement of mobility post plantar electrical stimulation intervention. In this study we will use a power of 80%, two –tailed t-test, and alpha level of 5% to observe a significant improvement in the intervention group receiving active stimulation compared to sham group (with nonfunctional stimulator), 18 subjects per group is required. Assuming a 10% drop out, the estimated sample size would be 20 subjects per arm. We recognize that this sample size may not be sufficient to validate all primary and secondary outcomes, but would be sufficient to estimate trend and estimate the sample size for follow up study. Upon approval of the sponsor, availability of budget, and based on initial results (first 20 subjects), the sample size may be increased as well.

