### **Statistical analysis:**

Continuous variables are expressed as mean +/- standard deviation (SD). Unpaired t-tests, Mann-Whitney U-tests, and Chi-square-tests will be used for baseline comparison according to the scale of the investigated variable and the distribution of the data. Repeated measures ANOVA tests will be used for examining the effect of intervention in each group after adjusting by age and BMI. Similar test will be used for short-term effect (i.e. changes in skin perfusion immediately after electrical stimulation) and long term benefit (i.e. changes in primary and secondary outcomes after 4 weeks). To account for missing data (prevent entire subject data removal due to lack of a data point), a linear mixed-effect model will be selected instead of univariate general linear model repeated measures analysis. T Chi-square-test will be used for comparing the incident of AE between groups. The effect size to discriminate between groups will be estimated using Cohen's *d* effect size and represented as *d* in the results section. Values ranging from 0.20 to 0.49 indicate small; from 0.50 to 0.79 indicate medium, from 0.80 to 1.29 indicate large, and above 1.30 indicate very large effects. Values less than 0.20 are considered as having no noticeable effect. Spearman correlation of coefficient will be used to examine association between changes in motor parameters and changes in skin perfusion and plantar sensation post intervention. All analyses will be performed using SPSS statistics (version 24; IBM, Armonk, NY, USA) , with a significance level of  $p < 0.05$ .

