**Title: ELECTRICAL STIMULATION AS AN ADJUNCTIVE THERAPY TO ACCELERATE WOUND HEALING
IN PEOPLE WITH PERIPHERAL ARTERIAL DISEASE AND PLANTAR ULCERS & A RANDOMIZED
CONTROLLED TRIAL**

Identifier: NCT03821675

Date: 10/8/2021

Statistical analysis plan

Continuous data were reported with mean \pm standard deviation (SD). Categorical data were presented as count (%). Shapiro-Wilk test was conducted to identify the normal distribution of continuous variables. One-way ANOVA for normally distributed variables or Mann-Whitney U test for non-normally distributed variables was used to estimate differences of mean between control and intervention groups. χ^2 test was used to determine significant level between the groups for categorical variables. The effect size was measured using OR and 95% CI for categorical variables, and Cohen's d to discriminate the difference of primary and secondary outcomes between groups. Outcome changes were assessed over time compared to BL within (ie, time effect) and between (ie, time \times group effect) groups using linear mixed model for normally distributed outcome and generalized estimating equations for non-normally distributed outcome with adjustment for potential confounders. Least significant difference method was used for multiple pairwise comparisons. Pearson and Spearman correlation analysis were performed to assess the relationship between wound or demographics/clinical characteristics, and vascular outcomes. The level of statistical significance was set at $P < .050$. To detect changes in perfusion in individuals with marked limb ischemia, a sub-analysis of patients with moderate to severe peripheral arterial disease (PAD) (ABI < 0.8 or > 1.4 at BL)²⁴ was performed. To detect associated risk comorbidities influencing wound healing in those healers (defined as $\geq 50\%$ of area reduction)²⁵ vs non healers under E-stim, a sub-analysis in the IG was also performed.

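### Aim 2's H4 turns an open list of secondary outcomes into an efficacy hypothesis tested at .05 each, with no order, error control across outcomes or exploratory label

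*Protocol*

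**What the plan says.** Aim 2 names two primary outcomes: speed of wound healing and plantar sensation. The rest are introduced this way: "Secondary outcomes include patients self-report outcomes (e.g., pain, sleep quality, and quality of life), changes in mobility (e.g. physical activities and gait"; adverse outcomes follow, also by example. H4 of Aim 2 then reads: "Patient-reported outcomes and other secondary outcomes will be improved in the active group". Unlike H2, it does not say that the comparison is with sham.

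The Purpose section has its own list of hypotheses, worded as efficacy statements. One concerns pain; another is "TENS is effective to improve mobility". The opening of Study Design repeats pain relief and mobility as things whose efficacy is tested, and the end of Background hypothesises better balance and mobility.

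The protocol's Statistical analysis section applies one method to "changes in primary and secondary outcomes after 4 weeks" at p < 0.05. The SAP sets the same level and assesses change both within groups (time effect) and between groups (time by group). Its only statement on multiplicity is "Least significant difference method was used for multiple pairwise comparisons".

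The limiting text is in Sample size estimation: "We recognize that this sample size may not be sufficient to validate all primary and secondary outcomes". The sentence goes on to say that the size is enough to gauge a trend and to plan the size of a later study.

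**The concern.** Four features combine. The secondary family is open-ended, it is the subject of a numbered hypothesis, every member is tested at the full .05 level, and nothing makes a secondary claim depend on the primary result. Following the plan as written, an investigator could find one secondary P value below .05 and report it as support for H4, even if neither primary outcome showed a difference.

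At stake is what the trial may conclude about pain, sleep, quality of life and mobility. The primary analysis is not affected.

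**Working it through.** **The plan's own figure.** There is none to reproduce. The documents state no familywise error rate and no number of secondary tests. The Aim 2 sample size does not enter, because the false-positive rate of a valid test under no effect does not depend on the number of subjects.

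**Inputs from the documents**
- Level per test: 0.05 (SAP; protocol, Statistical analysis). It is two-sided according to Sample size estimation ("two –tailed t-test, and alpha level of 5" percent). The chance of a false result in favour of active on one outcome is therefore 0.05 / 2 = 0.025.
- Direction: H4 predicts improvement in the active group, so the favourable direction is the relevant one.

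**Inputs that are assumptions**
- Number of outcomes, k. The low case is k = 5, the efficacy examples named in Aim 2: pain, sleep quality, quality of life, physical activity and gait. The high case is k = 12: the six questionnaires in the Schedule of Events (MOCA, FES-I, CES-D, PSQI, TSFI, PROMIS Global) plus VAS pain, activity, gait, balance and two perfusion measures, 6 + 6 = 12. The second count is this review's; the documents do not state it.
- Correlation between test statistics, ρ: a common value of 0, 0.5 or 0.8.
- Decision rule: any one significant secondary outcome is taken as support for H4.

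**Independent tests (ρ = 0)**
- In favour of active, 1 − 0.975^k: for k = 5, 1 − 0.8811 = 11.9%; for k = 12, 1 − 0.7380 = 26.2%.
- In either direction, 1 − 0.95^k: for k = 5, 1 − 0.7738 = 22.6%; for k = 12, 1 − 0.5404 = 46.0%.

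**Correlated tests.** With equally correlated normal test statistics, the chance of at least one result in favour of active is 1 − ∫ Φ((1.96 − √ρ·x)/√(1 − ρ))^k φ(x) dx. For either direction, Φ((−1.96 − √ρ·x)/√(1 − ρ)) is subtracted inside the power. Numerical integration gives:

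| k | ρ | In favour of active | Either direction |
|---|---|---|---|
| 5 | 0 | 11.9% | 22.6% |
| 5 | 0.5 | 9.1% | 18.3% |
| 5 | 0.8 | 6.4% | 12.7% |
| 12 | 0 | 26.2% | 46.0% |
| 12 | 0.5 | 16.0% | 31.9% |
| 12 | 0.8 | 9.3% | 18.6% |

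Against the nominal 2.5%, the favourable-direction range is 6.4 / 2.5 = 2.6 times to 26.2 / 2.5 = 10.5 times.

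**Not a ceiling.** Twenty independent outcomes would give 39.7% in favour of active. Repeated visits would add further chances. Reading H4 as a change from baseline within the active group would do so too, and such a change can occur under standard wound care without any device effect.

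**The case against.** The strongest reply is that the protocol already limits these outcomes. It separates primary from secondary, and the sample-size section says that the trial may not validate all of them and serves to estimate a trend and size a follow-up study. Read whole, that sentence is close to an exploratory qualification. A reader might infer that it concerns power alone, but its second half states a purpose, so that inference goes too far. What remains is that the limit appears only in the sample-size section, covers primary and secondary outcomes alike, and is not carried into H4, the Statistical analysis section or the SAP.

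Second, H4 speaks of the outcomes collectively, and no text says that one significant result satisfies it. That stands: the calculation uses the loosest reading. But the plan states no rule for deciding H4, so that reading is open.

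Third, a reader might count each quantity from the activity sensor (steps, postures, transitions) as a separate endpoint. The documents do not support that. They describe what the sensor records, the posture times come from one 48-hour record and depend on each other, and the activity, gait and balance measures are optional assessments that need not be done. That optional status may shrink the family, but it also leaves its membership unsettled.

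Fourth, the least significant difference statement concerns pairwise comparisons. It shows that the one multiplicity provision in the SAP does not reach across outcomes. It is not evidence of anything more.

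Finally, unadjusted secondary outcomes are common in a 40-subject study meant partly to plan another. That is fair, and it is why the request is for wording rather than a new design.

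**Conclusion.** The point holds. H4 and the pain and mobility statements are efficacy hypotheses over an open set of outcomes, tested at the same level as the primaries, without order, control across outcomes or an exploratory label.

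If any one significant secondary outcome counts as support, the chance of a false finding in favour of active is about 6% to 26%, and about 9% to 16% at correlation 0.5, against 2.5% for a single outcome. These figures rest on three assumptions: 5 to 12 outcomes, a common correlation between 0 and 0.8, and the any-one rule. The documents give none of the three.

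A reader might infer a 13% to 46% chance of a spurious efficacy claim. That range counts significance in either direction, including results that favour sham, whereas H4 predicts improvement. It also shares the same assumptions, and its upper end needs twelve independent tests, which is unlikely for related questionnaire and sensor measures in the same patients.

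**What to change.** - **Study Design (Aim 2), Statistical analysis and SAP:** state that the secondary outcomes are exploratory, report week-4 active-minus-sham differences with 95% confidence intervals, and make no efficacy claim from their P values.
- **H4, and the pain and mobility efficacy statements in Purpose, Background and Study Design:** reword to match the trend-estimation purpose in the sample-size section. Without this, the exploratory label would contradict the stated aims.
- **Sample size estimation:** note that the mobility effect from the earlier study was used only for sizing, since Aim 2 is sized on an outcome that would now be exploratory.
- **If a pain or mobility claim is wanted:** name one measure of each and test them in a fixed order at .05, only after the primary analysis succeeds. Because Aim 2 has two primary outcomes, success must be defined first. This option is open only if the data have not been analysed. The SAP is written in the past tense, and the documents do not settle the matter. If analysis has taken place, only the exploratory label and interval reporting remain.

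The cost is wording in several sections of the protocol and in the SAP, with no change to enrolment or data collection. The downside is that an isolated secondary P < .05 can no longer be presented as proof of benefit.

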## **Study Device**

BEST™ (Bio-Electric Stimulation Technology) devices produce unique microcurrent impulses transmitted through the skin to interface with the internal peripheral nervous system for the purpose of therapeutic intervention. The BEST microcurrent output stimulation is a train of high-voltage, pulsed-current, damped, sinusoidal and asymmetrical pulses. BEST devices react to the body's response to the microcurrent stimulus. With each response, the electrical properties of the tissue change. These changes in the tissue characteristics result in changes in the output. The device detects changes and indicates relative tissue reaction responses in a cybernetic feedback loop. BEST products are controlled by a high-performance microcomputer chip, which uses Avazzia proprietary software. These hand-held devices are FDA-cleared for the symptomatic relief and management of chronic, intractable pain and adjunctive treatment in the management of post-surgical and post-traumatic pain (available by prescription). These non-invasive neuro-stimulation devices allow patients to take control of their pain management. Avazzia BEST products feature a tissue reaction response indication, making them superior to traditional TENS units. BEST products work on different neural paths than a traditional TENS.

Avazzia BEST device technology and modes including the Tennant Biomodulator® devices have been FDA-cleared as transcutaneous electro-nerve stimulators for pain relief since 2007.

- K062641 clearance for BEST-AV1 family of micro current Rx devices with LED display for pain relief including reaction technology. The Tennant Biomodulator® device is a BEST-AV1 device. These devices are cleared for symptomatic relief and management of chronic, intractable pain, and adjunctive treatment in the management of post-surgical and post-traumatic pain (prescription required).
- K123099 clearance for BEST-AV2 professional family of Rx devices with LCD displays for pain relief including reaction technology. The Tennant Biomodulator PRO® device is a BEST-AV2 device. The difference between BEST-AV1 and BEST-AV2 is either LED display or LCD display of modes, power setting, timer, and reaction indications. The

BEST-AV2 devices have the same output specifications and technology as well as the same indications for use as the Rx devices in K062641.

- K162392 clearance for BEST-AV1 family of microcurrent devices with LED display for pain relief including reaction technology for Over-the-Counter use. They have the same output specifications and technology. The difference between Rx and OTC labeling is indication for use for temporary relief of pain associated with sore and aching muscles in the shoulder, waist, back, back of the neck, upper extremities (arm), and lower extremities (leg) due to strain from exercise or normal household work activities

The professional device with the LCD display will be used in the clinic, and patients will be issued the simpler device for home use.

*Tennant Biomodulator PRO® designed by AVAZZIA*

[figure not shown]
The candidate Tennant Biomodulator PRO® and the Tennant Biomodulator® devices designed by AVAZZIA are microcurrent transcutaneous electro-stimulation device with proprietary frequency sets specified by [name] MD within the BEST platform control options. The devices are easy-to-use, handheld, AA battery-operated portable device for use in the home or clinic. They apply charge and power to the tissue through electrodes where maximum power delivered to the load is controlled and limited, and an automatic shut off is implemented. The user can passively place the electrodes where indicated and apply stimulation for a period of time. The user controls the output by selecting the preset mode and power setting. The device's controls and visual indicators are located on the upper side of the case and on the upper cover.

Both Tennant Biomodulator® devices designed by AVAZZIA are indicated for:

- symptomatic relief and management of chronic, intractable pain
- adjunctive treatment in the management of post-surgical and post-traumatic pain

Tennant Biomodulator PRO® device	Tennant Biomodulator® device
 
The image shows the Tennant Biomodulator PRO device. It has a blue and black casing with a small LCD screen at the top displaying '3 13:17 TEN-8'. Below the screen are several control buttons and the AVAZIA logo at the bottom.
	 
The image shows the Tennant Biomodulator device. It has a black casing with a large LED display area. The display shows a blue and white graphic with a path of colored dots and labels for 'POWER' and 'MODE'. Below the display are four mode options: Assess, Ten-8™, Infinity, and Automatic. The AVAZIA logo is at the bottom.


Features:
 
 
• LCD display
 
• Over 50 present modes including Ten-8 and Infinity modes
 
• User programmable control settings including frequency, pulses per packet, time between pulses, modulation, damping output.
 
	
Features:
 
 
• LED display
 
• For four present modes: Assess, Ten-8, Infinity and automatic.
 

This photo shows relative size:

**Randomization & Blinding**

This study will be designed as a double-blind randomized clinical model. Both patients and the treating podiatrist will be blinded. The study coordinator will be aware of the assignment (active device or sham device) by a guide provided by the sponsor. The guide will identify which devices are active or inactive.

The control group will receive an identical device but without active electrical stimulation output. The physician treating the wound as well as patients will be blinded to the type of device. Only the study coordinator will be aware of assignment (active device or sham device). The study coordinator will reveal the group to the participant during the last visit. At that time, the coordinator will ask the participant if they would like to continue with the therapy. If they agree, participants will be instructed to contact Avazzia Inc. to receive a device after the completion of the study phone interview (12 weeks).

Each unit will be coded with a unique identification number, and the study coordinator will reveal their status, placebo or electric stimulation, only at the end of data collection from the last patient. The PI and data analyzer will be able to match the status of the identification numbers with the corresponding units to analyze the data. Since participating patients will have moderate-to-severe peripheral sensory neuropathy, they will be unable to determine via “feeling” whether or not they were receiving electrical stimulation. Furthermore, the credibility of design is enhanced due to all enrolled patients being therapeutically naïve to the sensation of electrical stimulation.

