## Study Tasks:

Medical History: The presence of diabetes will be determined based on American Diabetes Association criteria. This will include: duration and type of diabetes, type of diabetes medication (insulin, oral, combination therapy, diet), previous history of foot ulcers, amputation (toe, foot), lower extremity bypass, lower extremity angioplasty, Coronary artery bypass surgery, cardiac angioplasty, arthritis, liver disease, osteoporosis, malignancy, and bone tumors. We will measure height and weight to determine body mass index (BMI). We will evaluate glycated hemoglobin, albumin and prealbumin at baseline. We will confirm PAD by measuring ABI.

Social Factors: We will evaluate the following factors: marital status, years of education, type of work, tobacco history (pack years, current smoker, current use of chewing tobacco, previous smoker, no tobacco history), drug history (current, previous history, or no history), and alcohol history.

BEST Therapy: The participant will be given an active Tennant Biomodulator PRO ® by the research staff. They will place the pads on the plantar area of the foot and provide therapy for one hour. At the end of the visit, the research staff will provide an active or sham Tennant Biomodulator ® to the participant for in-home therapy. The participant will have the ability of increasing/decreasing the intensity of the therapy with the Tennant Biomodulator ®. At each visit, the research staff will provide AA batteries to the participant for the device.

Peripheral Neuropathy: Neuropathy and its severity will be assessed using vibratory perception threshold (VPT) at the affected side. VPT will be evaluated at the distal great toe and fifth metatarsal head using a Biothesiometer.

Vascular Assessment: We will assess perfusion of the macro-circulation with arterial Doppler studies and microcirculation with Skin Perfusion Pressure measurements (SPP) at the affected side. We will use the SensiLase system (Väsamed) to measure SPP in mmHg. Ankle Brachial Index (ABI) will be also measured in the case of compressive vessel and if it was feasible (e.g. in non-hemodialysis patients) on the affected side. Additionally, we will use HyperView Imaging (HyperMed Imaging, Inc., TN, USA) or Kent Camera (Kent Imaging Inc., Calgary Canada) for surface tissue oximetry measurement.

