### **Informed Consent:**

In order to recruit or identify subjects, we will screen our patient charts for eligible subjects.

The subject will be fully informed about the study, and will verbalize understanding and voluntarily agree to participate with the guidelines as stipulated in the informed consent. The subject will be informed if he/she can withdraw from the study at any time without loss of benefits. Consent forms will be signed and dated by the subject and by the Principal Investigator or Investigators. The original (with patient's signature) will be maintained per policy. A signed copy of the consent form will be provided to the patient. Informed consent will be obtained prior

to performance of any study procedures. Subjects are given as much time as needed to ask questions and read over the consent.

Subjects will be recruited from the Co-I's own practice. He may get some referrals from his colleagues that work in the same clinic such as [name] and other collaborators. We have included a Waiver of Partial Consent to cover our screening process. The Co-I will identify eligible subjects and alert the coordinator. The coordinator will review all the details of the study with the subject and/or their family. If the subject agrees to participate in the study, they will be screened and then enrolled into the study.

Spanish speakers will be consented using a full Spanish version of the consent. We have Spanish speaking coordinators on staff that can receive consent from Spanish speaking patients.

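### No allocation concealment is described for Aim 2, and the coordinator who presents the study to candidates holds the key that identifies active and sham units

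*Protocol*

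**What the plan says.** On allocation, Study Design (Aim 2) says: "Eligible participants will be randomized (ratio: 1:1) to either active (active group, n=20) or sham (sham group, n=20) therapy group". That is the whole description of the randomization procedure. The section headed Randomization & Blinding deals with who is blinded, not with how the sequence is made or protected.

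On who knows the assignment, that section says: "The study coordinator will be aware of the assignment (active device or sham device) by a guide provided by the sponsor". It continues: "The guide will identify which devices are active or inactive". Study Design (Aim 2) also says that the coordinator knows the assignment. Each unit carries a unique identification number, and patients and the treating podiatrist are blinded.

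On recruitment, Informed Consent says: "The Co-I will identify eligible subjects and alert the coordinator". Then: "The coordinator will review all the details of the study with the subject and/or their family". And: "If the subject agrees to participate in the study, they will be screened and then enrolled into the study".

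On dispensing, Study Tasks (BEST Therapy) says that at the end of the visit, after an hour on an active clinic device, "the research staff will provide an active or sham Tennant Biomodulator ® to the participant for in-home therapy".

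The SAP says nothing on sequence generation or concealment.

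**The concern.** Concealment and blinding are separate protections. Blinding acts after assignment. Concealment acts before it, and keeps the next assignment unknown until the participant is irrevocably entered. The safeguards in this protocol (coded units, an identical sham, blinded patients and treating physician) are all of the first kind. A unit code hides nothing from the person who holds the guide.

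If knowledge of unit status influences when or how a candidate is brought in, or which unit is handed over, the arms can differ in prognosis from the start. By the time the home unit is issued, the Schedule of Events places wound photos, vibratory perception threshold, skin perfusion and the immediate perfusion response to active stimulation at that same baseline visit. These are plausible markers of the Aim 2 primary outcomes, speed of wound healing and plantar sensation. The protocol's Statistical analysis section adjusts for age and BMI. The SAP adjusts for potential confounders that it does not name. Neither reliably removes an imbalance created by selection on wound, perfusion or neuropathy status, or on an unrecorded clinical impression.

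**Working it through.** **Step 1: the passages side by side.**

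| Question | Answer in the documents | Where |
|---|---|---|
| Who identifies candidates? | The co-investigator | Informed Consent |
| Who presents the study? | The coordinator | Informed Consent |
| Who screens and enrols? | Not named (passive voice) | Informed Consent |
| Who can decode units? | The coordinator, from the sponsor's guide | Randomization & Blinding; Study Design, Aim 2 |
| Who issues the home unit? | Research staff, not further specified | Study Tasks, BEST Therapy |
| When is it issued? | End of the visit, after the active session | Study Tasks, BEST Therapy |
| How is the sequence made, and who holds it? | Not stated | – |
| Must a particular unit be issued next? | Not stated | – |

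The person who presents the study can decode every unit, and no step separates that knowledge from enrolment or dispensing.

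**Step 2: what steering could do.** The plan has no figure to reproduce here, so this is an illustration.

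Input from the protocol: 20 per arm and a two-sided 5% t-test (Sample size estimation). Assumed inputs: no true effect; a share *s* of participants is placed by whether their prognosis is above or below average; prognosis is standard normal and correlates *r* with the outcome.

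- The mean of the upper half of a standard normal is √(2/π) = 0.798, so fully steered arms differ by 2 × 0.798 = 1.596 SD.
- Prognosis difference between arms: D = s × 1.596. For s = 20%, 30%, 40%: D = 0.319, 0.479, 0.638 SD.
- Outcome shift: b = r × D. For r = 0.5: b = 0.160, 0.239, 0.319 SD.
- Noncentrality: b × √(20/2) = 3.162 b. For r = 0.5: 0.505, 0.757, 1.009.
- The false-positive rate is the two-sided rejection probability of the noncentral t with 38 degrees of freedom, critical value 2.024.

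| Correlation r | s = 20% | s = 30% | s = 40% |
|---|---|---|---|
| 0.2 | 5.4% | 6.0% | 6.8% |
| 0.3 | 6.0% | 7.3% | 9.1% |
| 0.5 | 7.8% | 11.4% | 16.6% |

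With no steering the rate is 5.0%. With 10% steering and r = 0.5 it is 5.7%.

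**Step 3: would the baseline table show it?** A difference of 0.319 SD in prognosis (s = 20%) reaches p < 0.05 with 20 per arm in about 17% of trials, even if prognosis were measured directly. It would usually be missed.

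**The case against.** A reader might infer that the coordinator selects and enrols participants, knows the next assignment, and chooses the unit. The documents do not say so. Candidates are identified by the co-investigator, the enrolment sentence names no one, and the home unit is issued by research staff. Informed Consent also mentions coordinators in the plural (for Spanish-speaking patients), so the key holder and the issuer could be different people. The guide is described as a key to devices, not as a list of upcoming assignments. Choosing a unit to suit the patient would be a departure from the stated 1:1 randomization. All of this stands, and it limits the point to a route that is left open. It does not close the route, because no division of roles, forced order of issue or custodian is specified.

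It can also be said that the SAP analyses change from baseline with a linear mixed model or generalized estimating equations and adjusts for potential confounders, so an unadjusted t-test is not the planned analysis. That is correct, and the table should be read as an illustration. Since the confounders are unnamed, and adjustment works only on what is measured, the SAP's wording does not replace concealment.

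The correlations and steering shares have no source in the documents. At the lower values the inflation is small.

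Finally, Sample size estimation acknowledges that the trial may not be large enough to validate all outcomes and would serve to estimate a trend and size a follow-up study. This lessens the weight of a single false-positive result. But a selection-biased estimate would also mislead the planning of that follow-up.

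**Conclusion.** The point holds as a gap in design: no concealment procedure is described anywhere, and the coordinator who presents the study can tell active from sham units. Steering is possible, not stated or demonstrated, and its size cannot be derived from the documents. Under the stated assumptions the false-positive rate ranges from 5.4% (r = 0.2, 20% steered) to 16.6% (r = 0.5, 40% steered), against a nominal 5%. Two further inferences are unsupported: that allocation was in fact subverted, and that the whole trial is affected. Aim 1 is not affected, because every participant receives the active clinic device in that part. The weakness should be corrected because analysis cannot reliably restore concealment once it is lost, and the correction costs little.

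**What to change.** 1. Have the sponsor's device-supply function, with no participant contact, hold the guide together with a 1:1 list of unit numbers in permuted blocks of varying size that are not disclosed to the site.
2. Release only the next unit number to the site, after consent, eligibility and all baseline measures are recorded. The site must issue that unit. The units are already individually coded, so the key is not needed to dispense them.
3. Amend the sentence in Study Design (Aim 2) and both sentences in Randomization & Blinding that give the coordinator knowledge of the assignment. They should say that no one at the site with participant contact knows it.
4. Reconcile the two statements in Randomization & Blinding on when status is revealed: at each participant's last visit, or only after data collection from the last patient. Use the later time. With staggered enrolment, arms revealed one by one would help predict later assignments within a block. The protocol links the last-visit reveal to asking about continued therapy, so that text must be made consistent too.

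Cost: a short amendment and a list kept by the sponsor, who already produces the guide. No extra patients, visits or site staff are needed. The downside is that participants learn their arm later and the site must request the code.

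The SAP is written in the past tense. If enrolment has closed, report how units were actually assigned, by whom and in what order, and state the lack of described concealment as a limitation.
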